The WELL Study (Wellness Education for Liver Health Study): Reducing liver disease in genetically predisposed adults

Version: 12-2-21
HUM00154361

Principal Investigator
[name]

Methodology:

We will examine the feasibility and acceptability of our four-month, online, dietary intervention among 40 adults with NAFLD from a high-risk subpopulation (rs738409-GG and rs738409-CG).

Participant recruitment, liver clinic evaluation, and inclusion

and exclusion criteria. We have already identified candidates from the Michigan Genomics Initiative using their electronic medical records including outpatient laboratory values that are homozygous for *PNPLA3* rs738409 and have elevated liver-function tests (median alanine aminotransferase above 35 international U/L). They have already consented to be re-contacted and are motivated participants interested in further research. The clinical characteristics of eligible participants are given in **Table 2**.

We will contact the pool of potentially eligible participants by sending them a postcard describing the study, either in an envelope or with mailing information directly on the postcard. We may also send a follow up letter or flyer describing the study, in an envelope with either a handwritten or a typed address. Potential participants may also receive a phone call. Interested participants will fill out a screening survey; study team members will review their medical records for exclusions and elevated liver function tests. Participants that appear to meet inclusion and do not have exclusion criteria, based on their survey and medical chart, (**Table 3**) and agree to participate will be referred to our liver clinic to be evaluated to rule out other causes of elevated liver function tests (such as medications or high levels of alcohol intake).

Participants who are taking blood glucose-lowering medications will be considered

Table 2. Clinical Characteristics of Michigan Genomics Initiative rs738409-GGs with elevated ALT

Characteristic	rs738409 GG
Participants	363
Male Sex	162 (45%)
Age	48 [27–65]
BMI	32 [27–37]
ALT	49 [42–65]

Values are given as either median and interquartile range or as N (%).

Table 3. Inclusion and exclusion criteria.

Inclusion	Exclusion
Age > 18	Non NAFLD causes of elevated liver function tests
MRI with liver steatosis but not cirrhosis	Pregnant
English speaking and access to internet	Recent decompensation/hospitalization

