
[figure not shown]
Participants may be ineligible after their blood tests and virtual visit. If no other cause of elevated liver function tests is found except for NAFLD and the patient meets inclusion with no exclusion criteria, the patient will attend their second appointment at the main Michigan Medicine hospital to receive a baseline standard-of-care, clinical liver MRI-derived proton density fat fraction test, the gold standard for non-invasive measurement of both hepatic steatosis, fibrosis, and cirrhosis. Prior to this appointment, participants of childbearing potential will be mailed a urine pregnancy test. They'll be instructed to take this test the day of their MRI and to send a photo of the result to the study email (they can write their result if they're uncomfortable with a photo).

Participants with a positive test will be asked not to come in for their appointment and will not be eligible for the trial. At the second appointment, participants will complete an MRI screening with the technicians and may be ineligible if they are unfit for an MRI. Those whose MRI shows steatosis, mild fibrosis, and early cirrhosis (F1-4), will be invited into the trial, as these are the patients for whom we may be able to reverse fibrosis with intervention. (See **Figure 1** for the full flowchart of the study.) If participants are ineligible after completing their MRI, they will be compensated \$20 via Amazon gift card. The “psychological self-report” listed in Figure 1 for baseline and 4-month assessments includes questions concerning health-related quality of life,[1] dietary intake, physical activity,[2, 3] food cravings,[4] stress eating,[5, 6] dietary-based social support,[7] and hunger.[8]

Participants who are eligible after their MRI and have completed all other baseline measurements will be mailed a digital scale. Participants must weigh themselves on this scale within two weeks of receipt, before being enrolled in the trial.

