Many of these measurements are standard of care for non-alcoholic fatty liver disease and will be charged to the participant’s insurance. Baseline and follow up virtual visits, the baseline clinical liver MRI, and all baseline and follow up blood tests (with the exception of the excess serum, excess whole blood, and the fasting insulin tests) will be charged to the participant’s insurance. Participants will be informed of this during the consent process and will be encouraged to check their plans to ensure they have coverage. The study will cover the costs of all other measurements and materials.

Figure 1. Flowchart of intervention study.

NAFLD standard of care. All participants will receive care at our NAFLD liver clinic; we will provide state-of-the-art care of and resources about NAFLD to all participants. An information packet will be provided to all participants at their baseline office visit that includes: 1) NAFLD disease information including diagnosis, clinical manifestations, natural history, and treatments; 2) NAFLD physical activity recommendations including walking programs and physical activity logs; 3) weight tracking logs; and 4) resources for exercise programs. [name], with gastroenterology fellows working with her, will provide all medical care. Adverse events will be routinely queried at each clinic visit and the study physicians will be on call in the case of an adverse event. All participants will be taught a VLCD diets using our validated online program.

Participants will have a baseline virtual visit with [name] in the liver clinic and, if they appear eligible, they will come back for an MRI. After all baseline measurements are completed and if participants are still eligible, they will be enrolled in the 4-month online program. This program will include weekly lessons, mailed materials, and the support of a dietary coach. Details are outlined below:

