Safety and medication management. Participants will be asked in a weekly survey about health symptoms or adverse events they've experienced and to report any medication changes they've made. Participants who report symptoms will be reached by email as soon as possible by the study coordinator or diet coach. Participants may be called if the health event seems urgent or severe. For severe or long lasting symptoms, participants will be encouraged to reach out to their primary care physician. Participants who are taking some blood glucose-lowering medications (metformin, DPP-4s, GLP-1 agonists, and Thiazolidinediones (TZDs)) will continue their medications as normal. Participants taking all other glucose-lowering medications will be asked to stop taking these medications at the start of the trial (PCPs will be informed of this change when participants begin the trial). All participants will be asked in the aforementioned weekly survey about their highest and lowest fasted and postprandial (2 hours after eating) blood glucose levels over the previous week. If participants report low glucose (fasting below 70 mg/dL or postprandial below 110 mg/dL), they should reach out to their physician and follow self-management guidelines (sent to them as part of week 1's intervention materials). If participants report more than two weeks of high blood glucose (180 mg/dL), [name] [name] will reach out to participants via email or phone about management and reach out to participant PCPs.

Outcomes and analyses. After 16 weeks of the VLCD program, participants will complete a series of follow up measurements. Participants will complete a virtual follow up office visit, a follow up self-report survey, track their food, weigh themselves on the scale we sent them, take an at-home urine pregnancy test (if of childbearing potential), and return for a MRI-derived proton density fat fraction test. All final measurements should be completed within 4 weeks of completion of the program. Additionally, the second MRI will be conducted on research machines and charged to the study. Participants will also have a fasting blood draw. Follow up blood tests will include: complete blood count with differential, comprehensive metabolic panel, prothrombin time, fasting glucose, hemoglobin A1c, fasting insulin, and a serum lipid panel.

Statistical Design:

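### Match the two PDFF scans: baseline is a clinical hospital MRI and follow-up is on research machines, so any systematic offset would bias the single-arm pre-post change

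*Combined protocol and SAP*

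**What the plan says.** Under participant recruitment, eligible patients attend the main hospital to "receive a baseline standard-of-care, clinical liver MRI-derived proton density fat fraction test". The billing paragraph before Figure 1 puts this scan among the items charged to insurance: "Baseline and follow up virtual visits, the baseline clinical liver MRI, and all baseline and follow up blood tests". Under Outcomes and analyses, the follow-up fat fraction is measured after 16 weeks, and "the second MRI will be conducted on research machines and charged to the study". The timing rule there is "All final measurements should be completed within 4 weeks of completion of the program".

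There is one arm. NAFLD standard of care says "All participants will be taught a VLCD diets using our validated online program". Statistical Design expects a 12% loss of liver fat with SD 6% and analyses the change with a one-sample Wilcoxon test at alpha 0.01, claiming 99% power. It adds that, if the loss were 24%, there would also be 99% power to show a loss greater than 12%. It does not say whether 12% is relative or in absolute PDFF points, or whether the test is one- or two-sided.

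The recruitment section calls the MRI test "the gold standard for non-invasive measurement of both hepatic steatosis, fibrosis, and cirrhosis", and Statistical Design says that pre-post fibrosis values will be reported.

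The supplied text does not mention a common scanner, field strength, sequence, reconstruction or reading method for the two scans, a cross-calibration, or an adjustment for machine.

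**The concern.** Read as written, every participant moves from a clinical to a research setting between the two scans whose difference is analysed. In a controlled trial, an offset common to both arms would largely cancel. Here no control change is available to subtract, and a one-sample test sees only the difference, so an instrument offset and a treatment effect look the same. A larger sample does not help, because the offset is a bias and not noise.

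The measured change also contains other non-diet influences. These include liver-clinic care, the packet's "NAFLD physical activity recommendations including walking programs and physical activity logs", and regression to the mean after selection on raised ALT and on "MRI with liver steatosis but not cirrhosis". Matching the scans does not touch these, but the machine component is one that planning can largely remove.

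What is at stake is the fat-fraction result, the only outcome with a power statement, and above all the size of loss that readers would carry forward. Pre-post fibrosis values share the exposure if they come from the same MRI.

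**Working it through.** **Inputs from the protocol.** n=40 (Methodology); expected loss 12, SD 6, alpha 0.01 and one-sample Wilcoxon test (Statistical Design). **Assumed, because the documents give no figure:** the offset, its direction, the baseline PDFF, two-sided testing, and normally distributed changes. Rejection rates come from simulating the signed-rank test with its exact null distribution.

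**1. The plan's own figure.** Standard error = 6/√40 = 0.95. Expected loss in standard errors = 12/0.949 = 12.6, against a two-sided critical value of 2.58. Power is above 99.99%, so the stated 99% is met. The point is one of bias, not of power.

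**2. How an offset enters.** Measured change = true change + (research offset − clinical offset). If the net offset b is constant on the difference scale, it passes one-for-one into the estimate. An offset of 2 is 2/0.949 = 2.1 standard errors and 2/12 = 17% of the expected loss.

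**3. No true change, offset in the direction of a decrease (plan's units, n=40).**

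| Offset b | Significant decrease, two-sided 0.01 | One-sided 0.01 |
|---|---|---|
| 0 | 0.5% | 1% |
| 1 | 6% | 9% |
| 2 | 27% | 37% |
| 3 | 65% | 75% |

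The 0.5% in the first row is the decrease half of a two-sided 1%. The same rates would apply to a comparison with 12 if the true loss were exactly 12. At b=2, a large-sample version of the test (two-sided rejection) gives 26% at n=40 and 94% at n=160, so recruiting more makes a false finding more likely.

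**4. True loss 12, opposing offset, tested against zero (plan's units, n=40).** Power is 99.97% at an offset of 6, 99.1% at 7, 91.6% at 8 and 65% at 9. The test against zero is robust here, but the estimate is not: an opposing offset of 6 halves the reported loss (12 − 6 = 6).

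**5. If 12% is a relative loss.** An offset of d PDFF points becomes 100·d/baseline percentage points for each participant, so it varies with baseline. At a constant baseline of 10, one point is 100·1/10 = 10 percentage points, which leaves 12 − 10 = 2 of the expected 12. Three models of baseline spread were tried: constant; normal with SD 40% of the mean and values below 5 redrawn; and the same with values below 5 set to 5. Redrawing raises the nominal means of 10, 15 and 20 to about 10.8, 15.6 and 20.6.

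| Nominal mean baseline PDFF | Power, true loss 12%, opposing 0.5 point | Same, opposing 1 point | False decrease, no true change, 0.3 point |
|---|---|---|---|
| 10 | about 99.9% or more | 3–27% | 65–75% |
| 15 | about 99.9% or more | 79 to over 99% | 27–40% |
| 20 | about 99.9% or more | 99–100% | 14–22% |

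At constant baselines of 10, 15 and 20, a 0.3-point offset moves the estimated loss by 3, 2 and 1.5 percentage points, which is 25%, 17% and 12.5% of the expected 12.

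**The case against.** The strongest reply is that the harm is hypothetical. Both visits name the same PDFF test, and the words clinical and research appear next to billing arrangements, so they need not mean different hardware or sequences. Figure 1 is not shown, and scan parameters may sit in an imaging document outside this short protocol. All of this stands. A reader might infer that the machines differ, or that the fat-fraction result is already biased; the documents support neither. What they do show is a stated switch of setting that coincides with time point, with no stated safeguard.

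A reader might also infer that the test against zero is unsafe. Step 4 shows that it tolerates large opposing offsets in the plan's units, and step 5 shows the same for half a point on the relative scale. The high false-positive rates need a true change of zero, or a true loss of exactly 12 compared with 12. That comparison is only a conditional power remark in Statistical Design and not clearly a planned test.

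It is also fair to say that one-for-one carry-over is exact only for a constant offset on the difference scale. A proportional error of 2% in the second scan would move a true 12% loss only to 1 − 0.88 × 1.02 = 10.2% or 1 − 0.88 × 0.98 = 13.8%.

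Finally, the stated aim is feasibility and acceptability, which this does not affect, and fibrosis is descriptive with no material change expected. That limits the stakes. It does not remove them, because the protocol powers and tests the fat-fraction change.

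**Conclusion.** The concern holds as a conditional bias risk that is worth removing. Machine setting is aligned with time point, matching is not stated, and the one-sample Wilcoxon test cannot tell an offset from a change. The existence, size and direction of an offset are unknown, and every offset and baseline used above is assumed.

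The main exposure is the estimated size of the PDFF loss. A conclusion that there was some loss is well protected in the plan's units. It is less so if 12% is relative, which is the more natural reading of the sentence: with a mean baseline near 10, one opposing point could hide a true effect, and 0.3 point could produce a false one. Weight and laboratory outcomes are not affected, and neither are the feasibility aims. The stated power figure is not in error. Confidence is medium, because imaging details may exist elsewhere; if matching is already intended, one sentence settles the point.

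**What to change.** In Outcomes and analyses, replace the sentence on the second MRI with text such as: *The second MRI will be charged to the study and will use the same field strength, PDFF sequence and reconstruction as that participant's baseline MRI, on the same scanner where practical. Both scans will be measured by the same method, and the scanner used for each will be recorded.*

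If some scans cannot be matched, report the size of the PDFF loss, and any MRI-derived fibrosis change, with that caveat. It would also help to state in Statistical Design whether 12% and 6% are relative or absolute, since fragility depends on it, but that is secondary.

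Cost: the wording and the scanner record cost almost nothing, and the study already pays for the second scan. Matched slots for up to 40 scans may cost more or be less convenient, and they must fit the 4-week window; the documents give no scan price or budget. Some baseline clinical scans may need to be re-measured by the common method. The baseline scan need not be moved or repeated.

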Able to consent and follow directions	Weight loss medication or procedures planned
No physical limitations	Type 1 diabetes, cancer, heart failure, kidney failure, Cushing's syndrome
Physician approval to participate	Vegan, vegetarian, or other dietary restrictions
Rs738409 homozygote	Decompensated liver disease
Able to attend in-person appointments in Ann Arbor	Metal implants/inability to receive MRI

eligible for the trial. However, participants taking insulin will be excluded from participation. If the study team finds that recruitment is too slow and excluding insulin is too restrictive, participants taking insulin will be considered for enrollment. These participants will receive extra attention by study physicians in terms of medication management. See **Safety and medication management** section below.

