Based on a previous, small, short-term trial without genetic biomarkers,[1] we expect patients enrolled in this program to lose 12% of their liver fat with a standard deviation of 6%. With a one-sample Wilcoxon test, this sample is 99% powered to detect such a decrease in MRI-derived fat fraction at $\alpha = 0.01$. Extrapolating from the epidemiological association of the rs738409-GG genotype with fatty liver in insulin-resistant patients,[2] the benefit in this group may be twice as high as in the general population (24%); if so, we would likewise be 99% powered to detect a reduction *significantly greater than* 12% at $\alpha = 0.01$.

One-sample Wilcoxon tests will likewise be used for post-program vs. baseline insulin resistance and body weight as secondary outcomes. We do not anticipate significant fibrotic differences after 4 months on this intervention, but will report pre-post liver fibrosis values. Baseline and post-program semi-structured interviews, as in Aim 1, will be used to assess satisfaction, adherence and dropout.

1. Reeve, B.B., et al., *Psychometric evaluation and calibration of health-related quality of life item banks: plans for the Patient-Reported Outcomes Measurement Information System (PROMIS)*. Medical care, 2007. **45**(5): p. S22-S31.
2. Craig, C.L., et al., *International physical activity questionnaire: 12-country reliability and validity*. Medicine & Science in Sports & Exercise, 2003. **35**(8): p. 1381-1395.
3. Kiernan, M., et al., *The Stanford Leisure-Time Activity Categorical Item (L-Cat): a single categorical item sensitive to physical activity changes in overweight/obese women*. International journal of obesity (2005), 2013. **37**(12): p. 1597.
4. Dalton, M., et al., *Preliminary validation and principal components analysis of the Control of Eating Questionnaire (CoEQ) for the experience of food craving*. European journal of clinical nutrition, 2015. **69**(12): p. 1313.
5. Tsenkova, V., J.M. Boylan, and C. Ryff, *Stress eating and health. Findings from MIDUS, a national study of US adults*. Appetite, 2013. **69**: p. 151-155.
6. Burgess, E., et al., *Profiling motives behind hedonic eating. Preliminary validation of the Palatable Eating Motives Scale*. Appetite, 2014. **72**: p. 66-72.
7. Norman, G.J., et al., *Reliability and validity of brief psychosocial measures related to dietary behaviors*. International Journal of Behavioral Nutrition and Physical Activity, 2010. **7**(1): p. 56.

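### A reduction above 12% in this single-arm study cannot be read as greater benefit in GG carriers, and the stated alpha of 0.01 does not cover that comparison

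*Combined protocol and SAP*

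**What the plan says.** The Statistical Design section derives its reference value as follows: "Based on a previous, small, short-term trial without genetic biomarkers", the plan states, "we expect patients enrolled in this program to lose 12% of their liver fat with a standard deviation of 6" percent. The first power claim tests this loss against zero: "With a one-sample Wilcoxon test, this sample is 99% powered to detect such a decrease in MRI-derived fat fraction", at alpha 0.01.

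A second claim follows. From an epidemiological association between GG genotype and fatty liver, the plan reasons that the GG benefit may be double, at 24%. It adds that "the benefit in this group may be twice as high as in the general population (24%); if so, we would likewise be 99% powered", again at alpha 0.01, to find a reduction exceeding 12%. The one-sample Wilcoxon is the only test named, and its sidedness is not stated.

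The study has one arm. Under NAFLD standard of care, all participants are taught the same diet, and those still eligible after baseline measurements go forward together: "they will be enrolled in the 4-month online program".

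The documents disagree on genotype. The opening of Methodology describes a "dietary intervention among 40 adults with NAFLD from a high-risk subpopulation (rs738409-GG and rs738409-CG" population, whereas Table 3 lists "Rs738409 homozygote" as an inclusion criterion. No GG-only or GG-versus-CG analysis is described.

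**The concern.** The second power claim sets a null value, an alpha and a power for a statement about GG carriers, and it describes 12% as what the general population gains. No other analysis in the plan bears on genotype. A significant result would therefore naturally be read as showing that carriers gain more.

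A one-sample test does not support that reading. It asks whether the mean in this sample exceeds a number. It does not ask whether carriers respond differently from non-carriers given the same program. The number is itself an estimate, from patients of unknown genotype in another trial. The 24% comes from an association with disease, not with treatment response, so it gives no independent support. At stake is a claim of genotype-specific benefit carrying an error rate that was never calculated for it.

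**Working it through.** **Inputs.** n = 40 (Methodology); expected loss 12%, SD 6%, alternative 24%, alpha 0.01 (Statistical Design). No separate SD is given for the 24% scenario, so 6 is used. The size, standard error and length of the earlier trial are not given. The citation number attached to it matches a quality-of-life item-bank paper in the reference list, so the list does not supply them either. Let m be its assumed size.

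**1. The plan's own figure.** Both claims involve a shift of 12 with SD 6. Standard error = 6/√40 = 0.949, and 12/0.949 = 12.65. Power = Φ(12.65 − 2.576), which is above 0.9999 two-sided, and higher one-sided. Simulation with exact signed-rank critical values agrees, and the one-sided test keeps its level (0.00999). The stated 99% is met, and it would still be met with SD 12 (power above 0.999).

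**2. What the test can be attributed to.** A mean above 12% could arise without any genotype effect:
- The earlier trial is called only short-term, so its length may differ from 16 weeks.
- Its population may differ. Candidates here were identified by elevated ALT.
- The baseline MRI is clinical and the follow-up MRI uses research machines (Outcomes and analyses). Any systematic difference between them would enter the change.
- The 12% estimate may have been low by chance.

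Without a concurrent non-carrier group, none of these can be separated from genotype. If CG carriers are among the 40, the sample mean is not a GG mean.

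**3. Sampling error in the 12%.** Suppose there is no genotype effect, both trials share the same true mean, and SD is 6 in each. The test compares the sample mean with a benchmark that itself varies. The upward rejection rate is P(Z > z/√(1 + n/m)), with z = 2.326 one-sided (nominal 1%) or 2.576 for the upper tail of a two-sided test (nominal 0.5%). For n = 40:

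| m | 1 + 40/m | 2.326/√(1 + 40/m) | one-sided rate | upper tail, two-sided test |
|---|---|---|---|---|
| 10 | 5.00 | 1.040 | 14.9% | 12.5% |
| 20 | 3.00 | 1.343 | 9.0% | 6.9% |
| 30 | 2.33 | 1.523 | 6.4% | 4.6% |
| 40 | 2.00 | 1.645 | 5.0% | 3.4% |
| 100 | 1.40 | 1.966 | 2.5% | 1.5% |

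Signed-rank simulation gives one-sided rates of 13.9%, 8.2%, 4.7% and 2.3% at m = 10, 20, 40 and 100. If only 20 of the 40 were GG and the test used those alone, the formula gives 9.0%, 5.0% and 2.9% at m = 10, 20 and 40.

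**4. Systematic differences (illustrative).** If non-genetic factors alone put the true mean at 14% or 15%, the shift in standard errors is 2/0.949 = 2.11 or 3/0.949 = 3.16. The one-sided test then rejects in about 37–39% or 75–77% of trials (27–29% or 65–67% two-sided). The lower figures are from signed-rank simulation, the higher from the noncentral t.

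**5. Sampling error alone is not decisive.** The one-sided threshold against a fixed 12% is 12 + 2.326 × 0.949 = 14.2%. Allowing for m = 10, it is 12 + 2.326 × 6 × √(1/40 + 1/10) = 16.9%, still well below 24%.

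**6. A within-trial comparison.** With 20 GG and 20 CG (an assumed split) and SD 6, SE = 6 × √(2/20) = 1.90. For 99% power at two-sided 0.01, the difference must be (2.576 + 2.326) × 1.90 ≈ 9.3 points. A difference of 6 gives Φ(6/1.90 − 2.576) ≈ 72%, or about 67% with the t distribution.

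**The case against.** The strongest reply is that the plan makes a narrower claim. The sentence is conditional, it concerns exceeding 12%, and for that question the alpha and power are right. The stated purpose is feasibility and acceptability, and nowhere does the plan commit to concluding that genotype causes a larger response. This stands as a reading of the words. It does not remove the difficulty, because the same sentence identifies 12% with the general population and gives the GG association as the reason to expect more.

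The documents do not support several stronger readings that a reader might infer:
- That the 99% power or the alpha is miscalculated. Neither is, against a fixed 12%.
- That sampling error in the 12% by itself prevents a demonstration of extra benefit. If 24% and SD 6 were true, a comparison carrying both trials' errors would still have about 95–97% power at m = 5 and over 99% at m = 10.
- That the two programs are known to differ in length. A four-month trial could also be called short-term, so the 14% and 15% scenarios are illustrations only.
- That a GG-versus-CG contrast would be powered almost with certainty. That assumes CG carriers lose only 12%, although the plan places them in the same high-risk group, where an intermediate response is plausible.

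**Conclusion.** The point holds as one about inference. The planned test is valid against a fixed benchmark of 12%, but it is not evidence of greater benefit in GG carriers. The main reasons are the missing concurrent comparator, the unresolved genotype criterion, and possible differences in length and population from the earlier trial. Sampling error in the benchmark is secondary. It puts the one-sided false-positive rate for the comparative claim between about 15% (m = 10) and 2.5% (m = 100), against a nominal 1%. That range assumes normal data, SD 6 in both trials, n = 40 with no dropout, and no true difference between the populations. How large the inflation is cannot be settled without the size of the earlier trial. A reader should not take any single multiple of 0.01 as established, although the rate is at least three times nominal for any m up to 75.

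**What to change.** 1. Report the change in fat fraction in GG participants with a 99% confidence interval. State that 12% is a descriptive benchmark and that exceeding it is not a test of genotype benefit.
2. If a comparison with the earlier trial is kept, give that trial's size and length, include its standard error, and call the comparison descriptive.
3. Reconcile the opening of Methodology with Table 3 on genotype. If CG participants are enrolled, make the within-trial GG minus CG difference in change, adjusted for baseline fat fraction, the genotype comparison. Participants in both groups share the same program and MRI schedule, so those effects largely cancel. Give it its own power statement for the expected split, using the figures in step 6 of the working as a guide.

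The cost is some wording in the statistical section and a modest change of analysis, with no new data collection. The price is a wider interval and a more cautious claim. By the normal formula, the 99% half-width grows from 2.576 × 0.949 = 2.4 points against a fixed 12% to 2.576 × 6 × √(1/40 + 1/10) = 5.5 points if the earlier trial had 10 patients.
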